Cost-effectiveness analysis (CEA) and cost-benefit analyses (CBA) will be carried out for HEV vaccine delivery to women in this setting taking the societal perspective (Cartwright, 2005). The cost of vaccination will thus be estimated and compared with its outcomes in terms of health gain (DALYs averted/QALYs gained) and economic gain (cost-saved from the society) (Manca et al. 2015; Murray and Lopez, 2013). Cost of vaccination (total cost, cost per vaccinated woman, marginal cost for vaccination) will be calculated for applying in both CEA and CBA. Costing of any intervention is concerned about systematic collection of information about resources used, categorizing the resources and analysing their costs (Drummond et al. 2005). Ingredient and budgetary approach will be utilized for this costing exercise considering the program perspective. All inputs, for instance, staff time, use of space, medical equipment, shared administrative costs, will be identified by visiting the site, interviewing the relevant key personnel and reviewing the documents of the vaccination program. Identified inputs will then be classified into capital and recurrent items as well as into fixed and variable items. Annuity of capital items (like, medical equipment, computer) will be done using the lifetime of such items for estimating their annual equivalent costs. In order to adjusting for the differential in timing of resources used, discounting rate of 3% will be applied for base analysis and 0% and 5% for sensitivity analysis. Cost per vaccinated will be calculated by dividing the total costs with the total number of vaccinated women.

Feasibility and acceptability of the vaccine

Operational feasibility of introduction of HEV vaccine will be assessed by in-depth interviews with health workers (15-20) (who will motivate women to bring to the health centre for vaccination) and health care providers (15-20) (providing vaccines to the study women). These interviews will help to identify operational barriers in motivating women for vaccination and in the storage and administration of vaccines. Acceptability of the vaccine will be assessed by conducting in-depth interviews with vaccine acceptors and non-acceptors. A total of 30-40 interviews will be conducted - half of which will be conducted with acceptors and the rest will be conducted with the non-acceptors.

Organization of the study

Study coordination

NIPH

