For cost-effectiveness analysis, cost per DALY averted and QALYs gained will be compared with Gross-Domestic Product per capita threshold for classifying the intervention into very cost-effective, cost-effective and not cost-effective. The vaccination program will be very cost-effective, cost-effective or not cost-effective if the cost-effectiveness ratio estimate is 1, 2 and 3 times less than the GDP per capita of the reporting country cost-effectiveness ratio (WHO 2003).

For cost-benefit analysis, the monetary benefits will be calculated by estimated costs saved (corresponding to cost of illness) due to HEV infection aversion through vaccination. Net benefit (total benefits minus total vaccination cost) and benefit-cost ratio (BCR) will be calculated, where positive value of net benefit and value more than 1 of BCR will indicate the acceptability of the vaccination against HEV.

The cost analysis will give the opportunity for modelling the costs for scaling up the vaccination program on the national level.

Data Safety Monitoring Plan (DSMP)

All clinical investigations (research protocols testing biomedical and/or behavioural intervention(s)) should include the Data and Safety Monitoring Plan (DSMP). The purpose of DSMP is to provide a framework for appropriate oversight and monitoring of the conduct of clinical trials to ensure the safety of participants and the validity and integrity of the data. It involves involvement of all investigators in periodic assessments of data quality and timeliness, participant recruitment, accrual and retention, participant risk versus benefit, performance of trial sites, and other factors that can affect study outcome.

Data Safety and Monitoring

A Data Monitoring Board (DSMB) will be tasked with monitoring the conduct of the trial, review the accumulating trial data and in particular reports of SAEs (related and not related, irrespective of severity) and make recommendations as appropriate. The study will be discontinued according to a priori defined stopping rules.

Ethical Assurance for Protection of Human rights

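### The cost-effectiveness rule gives all three classes an upper limit, so the classes overlap and leave high ratios unclassed; the costing perspective also needs reconciling

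*Combined protocol and SAP*

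**What the plan says.** The Statistical Analysis section compares cost per DALY averted and per QALY gained with GDP per capita, as a "threshold for classifying the intervention into very cost-effective, cost-effective and not cost-effective". The next sentence gives the rule. It names the three classes in that order and ends "not cost-effective if the cost-effectiveness ratio estimate is 1, 2 and 3 times less than the GDP per capita", followed by a reference to a country ratio that has no clear meaning there, and a citation of the 2003 WHO guide. No other section states cut points.

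For the cost-benefit analysis, the same section says that "monetary benefits will be calculated by estimated costs saved (corresponding to cost of illness") averted by vaccination. It adds that "Net benefit (total benefits minus total vaccination cost) and benefit-cost ratio (BCR) will be calculated", and that a "positive value of net benefit and value more than 1 of BCR will indicate the acceptability of the vaccination against HEV".

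The Economic analysis section says that both analyses are done "taking the societal perspective", with the gain described as "economic gain (cost-saved from the society"). The ingredient and budgetary approach, however, "will be utilized for this costing exercise considering the program perspective". The resulting vaccination cost is to be used in both analyses. The inputs it names as examples are staff time, space, equipment and shared administration. They are to be identified from site visits, interviews with key personnel and programme documents.

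**The concern.** A classification rule must give each possible ratio exactly one class. This one attaches a less-than condition even to the unfavourable class, which should be open at the top. It also offers three multipliers where three classes need two boundaries. If the sentence stays as it is, someone has to decide what it means once the ratio is known.

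The second part concerns what the ratio is built from. If savings are counted for society and vaccination is costed only for the programme, net benefit and the benefit-cost ratio set quantities from two perspectives against each other.

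The stake is a secondary one, but the protocol gives it weight. Cost-effectiveness is among the listed hypotheses and secondary objectives, and the Rationale treats evidence of it as a precondition for using the vaccine in low-income countries. The Statistical Analysis section is the only place that says how the verdict will be reached.

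**Working it through.** **(a) The threshold rule.** There is no stated figure to reproduce, so the check is one of logic. Let r = cost-effectiveness ratio / G, which has no units. The inputs are the three classes, the multipliers 1, 2 and 3, and the less-than direction, all from the Statistical Analysis section.

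- Reading A, upper multiples: the classes require r < 1, r < 2 and r < 3.
- Reading B, k times less taken as division: the classes require r < 1, r < 1/2 and r < 1/3.
- For comparison, two complete rules with two cut points each: 1 and 2, or 1 and 3, with everything at or above the upper cut classed as not cost-effective.

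In the table, *very*, *CE* and *not* stand for very cost-effective, cost-effective and not cost-effective.

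| r | Reading A | Reading B | Cuts 1 and 2 | Cuts 1 and 3 |
|---|---|---|---|---|
| 0.25 | very, CE, not | very, CE, not | very | very |
| 0.4 | very, CE, not | very, CE | very | very |
| 0.75 | very, CE, not | very | very | very |
| 1.5 | CE, not | none | CE | CE |
| 2.5 | not | none | not | CE |
| 3.5 | none | none | not | not |

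Under A, every ratio below G meets all three classes, ratios from G to below 2G meet two, and ratios of 3G or more meet none. Under B, ratios below G/3 meet all three and ratios of G or more meet none. Under neither reading are the classes exclusive, and under neither do they cover every ratio.

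The two complete rules differ only for 2 ≤ r < 3. The sentence points both ways there. Pairing multipliers with classes in order puts the end of the middle class at 2G. But attaching 3 to the unfavourable class makes sense only if that class starts at 3G.

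**(b) The perspective.** Side by side, the Economic analysis section gives:

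- Perspective of both analyses: society.
- Gain: savings to society.
- Vaccination cost: the programme's perspective, with only provider-side examples named.
- Use of that cost: both analyses.

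The protocol also has women come to fixed site clinics for a three-dose schedule, with 30 minutes of observation after each dose. Their travel and time are therefore real inputs to a societal costing, yet no section mentions them.

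Let V be the programme cost, B the estimated benefit, P any participant cost left out and D any benefit left out.

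- Net benefit: reported B − V; complete (B + D) − (V + P). Reported minus complete = P − D.
- Benefit-cost ratio: reported B/V; complete (B + D)/(V + P). The reported ratio is too high only if B(V + P) > V(B + D), that is, if P/V > D/B.

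The documents give no value for V, B, P or D. With D = 0 and P > 0 both measures favour vaccination too much; with D large enough the error disappears or reverses.

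**The case against.** On (a), the strongest reply is that this is a drafting slip in a rule tied to a cited source. The WHO guide is in the reference list, so the cut points are to be copied from it and not invented later. The numerical ratio can be reclassified by any reader, the candidate rules disagree only between 2G and 3G, and nothing suggests the result will land there. The separate cost-benefit criteria are clear. Most of this stands, and it is why the severity is low. It does not rescue the sentence, which is the only rule the plan states and cannot be applied as printed.

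A reader might infer that the rule reverses the labels, so that the cheapest programme would be called not cost-effective. The text does not support that: under reading B the lowest ratios meet all three conditions, and a reversed order appears only if one adds a precedence rule the protocol does not give. Nor can one conclude that the upper cut point stays undetermined once the guide is followed, because the guide is not among the documents.

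On (b), the reply is that a programme costing can be one component of a societal analysis, and that the inputs are introduced as examples, so nothing expressly excludes the women's costs. This stands. A reader might infer that the analysis omits those costs and is therefore biased towards vaccination. Neither step is established: the omission is not stated, and benefits are described only as illness costs saved, so the benefit side may be incomplete too.

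**Conclusion.** Part (a) holds as an error in the wording of a decision threshold. On either reading the three classes overlap at low ratios and leave high ratios unclassed (3G or more, or G or more). The practical ambiguity between sensible rules is confined to ratios from 2G to below 3G. This rests only on taking the less-than conditions at face value.

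Part (b) holds as an inconsistency to reconcile, not as a demonstrated bias. If the women's costs are left out while savings to society are counted, net benefit and the benefit-cost ratio mix perspectives. The size is unknown, and the net direction depends on whether P exceeds D, or P/V exceeds D/B.

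Both parts concern a secondary economic objective that is not among the listed secondary endpoints. The primary analysis and the sample size are unaffected. Severity is low.

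**What to change.** (a) Before analysis, replace the sentence with a rule that has two ascending, mutually exclusive cut points, taken from the WHO guide the protocol cites. Class everything at or above the upper one as not cost-effective. Report the numerical ratios (per DALY and per QALY) as multiples of GDP per capita next to the class. This costs one rewritten sentence.

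(b) Use one perspective for costs and savings, and state which benefits are given a monetary value. There are two ways:

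- Relabel the analysis as programme perspective and count only programme or health-system savings. This is a wording change plus a narrower benefit count, and the societal claim is given up.
- Keep the societal perspective and add participant travel and time to the vaccination cost. This needs a few cost questions to a sample of women. The General Study Design section already speaks of an ongoing study with blood samples taken, so the answers may have to rely on recall.

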Zhang J, Zhang X-F, Huang S-J, Wu T, Hu Y-M, Wang Z-Z, et al. Long-Term Efficacy of a Hepatitis E Vaccine. *New England Journal of Medicine*. 2015;372(10):914-22.

Gender Framework

In Relation to HEV:	Are there sex differences in	How do biological differences between women and men influence their :	How do the different roles and activities of men and women affect their	How do gender norms / values affect men and women's	How do access to, and control over resources affect men and women's
Vulnerability: Incidence Prevalence (male/female)	No significant sex difference reported in incidence or prevalence of HEV. Severity of infection increases in pregnancy	Nothing.	Men may drink more contaminated food and water from outside of their homes/work place. They may have higher chance of infection	Due to job nature men may be more exposed to infection and chance of developing diseases	
Health seeking behaviour	Men may seek care from hospital/medical practitioners while women mostly from traditional healers	Nothing known	Men may work outside and take care from health services	In many cases men get priority because of higher status.	Economic factors are responsible in seeking treatment. Women have little control over household income. They may be non-user of services.
Ability to access health services	Men have more access to health services	Not applicable		Routine treatment of hepatitis in pregnancy is hampered by the range of cultural, social and economic factors. Women more likely to use traditional healers	
Experience with health services and health providers	Female participants had more difficulty in getting services	Not applicable	Women, as mothers, are the target of programmes to get children to health centres	Women may refuse examination by male providers; resulting delayed diagnosis.	Gender, a factor because women have less control over household income
Preventive and Treatment options, responses to treatment or rehabilitation	Hepatitis E Vaccine is not licensed in many countries including Bangladesh. It is an	Non-involvement of women in vaccine trials may result	Women may have less in getting preventive and treatment care.	Preventive programmes are usually community based; where social norms mean that women cannot	Financial considerations are usually important whether a full course of treatment is completed – links to women's lesser access to income

In Relation to HEV:	Are there sex differences in	How do biological differences between women and men influence their :	How do the different roles and activities of men and women affect their	How do gender norms / values affect men and women's	How do access to, and control over resources affect men and women's
	effective vaccine in males.			participate;	
Outcome of health problem	Female mortality due to Hepatitis is higher than male. Death from Hepatitis E may occur 20-25% in pregnant women	Poor prognosis during pregnancy	Different studies have shown higher mortality among females	Biologically bad outcomes in females, may not be due to treatment seeking patterns	Poor outcomes for pregnant women
Consequences (economic & social, including attitudinal)	Economically affects the family as females are worst sufferer	Biologically bad outcome in females			Poor outcomes in females

Check-List

Check-list for Submission of Research Protocol For Consideration of the Research Review Committee (RRC) [Please check all appropriate boxes]

1. Has the proposal been reviewed, discussed and cleared by all listed investigators?

Yes No

If the response is No, please clarify the reasons:

2. Has the proposal been peer-reviewed externally?

Yes No External Review Exempted

If the response is 'No' or "External Review Exempted", please explain the reasons:

If the response is "Yes", please indicate if all of their comments have been addressed?

Yes (please attach)

No (please indicate reason(s)):

3. Has the budget been reviewed and approved by icddr,b's Finance?

Yes No (reason): _____

4. Has the Ethics Certificate(s) been attached with the Protocol?

Yes No

If the answer is 'No', please explain the reasons:

Signature of the Principal Investigator
